6.22.4. Overdose

An overdose is any dose of study drug given to a subject that exceeds the protocol specified dose by 10% or more. In the event of an overdose-associated AE, appropriate supportive therapy should be initiated according to the subject's signs and symptoms.

Any overdose, with or without associated AEs, will be promptly reported to the Sponsor and recorded as non-compliance on the eCRF. AEs associated with overdose should be reported on relevant AE/SAE sections in the eCRF.

6.22.5. Serious Adverse Events

6.22.5.1. Definition

A SAE is defined by federal regulation as any AE occurring at any dose that results in any of the following outcomes: death, life-threatening AE, in-patient hospitalization or prolongation of existing hospitalization, a persistent or significant incapacity or substantial disruption of the ability to conduct normal life functions, or a congenital anomaly/birth defect.

Important medical events that may not result in death, be life threatening, or require hospitalization may be considered an SAE when, based upon appropriate medical judgment, they may jeopardize the subject, and may require medical or surgical intervention to prevent one of the outcomes listed in this definition. Examples of such medical events include

allergic bronchospasm requiring intensive treatment in an emergency room or at home, blood dyscrasias or convulsions that do not result in inpatient hospitalization, or the development of drug dependency or drug abuse.

A life-threatening AE is one that, in the view of the Investigator, places the subject at immediate risk of death from the reaction as it occurred.

An unexpected AE is any event for which the specificity or severity is not consistent with the AE profile in the current EFX IB.

All SAEs, regardless of cause(s) or relationship to study drug, must be reported immediately to the study Sponsor and/or designee.

6.22.6. Reporting Adverse Events

6.22.6.1. Reporting Procedures for Non-Serious Adverse Events

The Investigator is responsible for ensuring that all AEs observed by the Investigator or designee or reported by the subject are reported using the AE eCRF.

The Investigator will assign the following AE attributes:

- AE diagnosis or syndrome(s), if known (if not known, signs or symptoms)
- Dates of onset and resolution (if resolved)
- Severity
- Relatedness to study drug or study-related procedures
- Action taken with study treatment

Follow-up of non-serious AEs will continue through the last day on the study participation and/or until a definitive outcome (e.g., resolved, resolved with sequelae, lost to follow-up) is achieved.

When a subject is withdrawn from the study because of a non-serious AE, the Sponsor and/or designee must be notified by e-mail or phone within 48 hours.

6.22.6.2. Reporting Procedures for Serious Adverse Events

The Investigator is responsible for ensuring that all SAEs observed by the Investigator or reported by the subject are promptly assessed and reported. The Investigator must assess whether the SAE is related to study drug or any study-related procedure.

The procedures for reporting SAEs are as follows:

Initial Reports

- All SAEs occurring after the ICF has been signed or during the study treatment and safety follow up periods must be reported to Labcorp Clinical Safety within 24 hours of the knowledge of the occurrence. After the protocol-specified reporting window,

any SAE that the Investigator considers related to study must be reported to Labcorp Clinical Safety or the Sponsor/designee.

- To report the SAE, complete the SAE form, indicating SAE criteria has been met, electronically in the electronic data capture (EDC) system for the study. If the event meets serious criteria and it is not possible to access the EDC system, fax/email the completed paper SAE form to Labcorp Safety at [contact] or [name] within 24 hours of awareness.
NOTE: any reports faxed to [name] will be routed to [contact]. When the EDC system becomes available, the SAE information must be entered within 24 hours.

Follow-Up Reports

- The Investigator must continue to follow the subject until the SAE has subsided or until the condition becomes chronic in nature, stabilizes (in the case of persistent impairment) or the subject dies.
- Within 24 hours of receipt of follow-up information, the Investigator must update the SAE electronically in the EDC system for the study, and submit any supporting documentation (e.g., subject discharge summary or autopsy reports) to Labcorp Clinical Safety via fax or e-mail. If it is not possible to access the EDC system, refer to the procedures outlined above for initial reporting of SAEs.
- The Sponsor or/or designee may request additional information from the Investigator to ensure the timely completion of accurate safety reports.

The Investigator must take all therapeutic measures necessary for resolution of the SAE. Any medications or therapies necessary for treatment of the SAE must be recorded in the AE form and the concomitant medication eCRF.

Follow-up of SAEs will continue through the last day on the study and/or until a definitive outcome (e.g., resolved, resolved with sequelae, lost to follow-up, fatal) is achieved.

If a subject becomes pregnant during the study or within the safety follow up period defined in the protocol, the Investigator is to stop dosing with study drug(s) immediately and the subject should be withdrawn from the study treatment. Early termination procedures and safety follow-up should be implemented at that time.

A pregnancy is not considered to be an AE or SAE; however, it must be reported to Labcorp Clinical Safety within 24 hours of knowledge of the event. Labcorp Clinical Safety will then provide the Investigator/site the Exposure In Utero (EIU) form for completion. The Investigator/site must complete the EIU form and fax/email it back to Labcorp Clinical Safety.

If the female partner of a male subject becomes pregnant while the subject is receiving study drug or within the safety follow up period defined in the protocol, the Investigator should notify Labcorp Clinical Safety as described above.

The pregnancy should be followed until the outcome of the pregnancy, whenever possible. Once the outcome of the pregnancy is known, the follow-up EIU form should be completed and faxed/mailed to Labcorp Clinical Safety. If the outcome of the pregnancy meets the criteria for immediate classification as an SAE (i.e., postpartum complication, spontaneous abortion, stillbirth, neonatal death, or congenital anomaly), the Investigator should follow the procedures for reporting an SAE.

Safety Contact Information:

Labcorp Clinical Safety

Facsimile: United States [name] (Global fax numbers located in Study Binder)

E-mail: [contact]

Some SAEs will qualify for reporting to the Food and Drug Administration (FDA) as applicable via the MedWatch/CIOMS reporting system in accordance with FDA and other applicable regulations. The Sponsor or its designee will report SAEs and/or SUSARs as required to regulatory authorities and Investigators in compliance with all reporting requirements according to local regulations and Good Clinical Practice (GCP).

Depending on relevant local legislation or regulations, including the applicable US FDA Code of Federal Regulations, the EU Clinical Trials Directive (2001/20/EC) and relevant updates, and other country-specific legislation or regulations, Akero may be required to expedite to worldwide regulatory agencies reports of SAEs, serious adverse drug reactions (SADRs), or SUSARs. In accordance with the EU Clinical Trials Directive (2001/20/EC), Akero or a specified designee will notify worldwide regulatory agencies and the relevant IRB/IEC/EC in concerned Member States of applicable SUSARs as outlined in current regulations.

The Investigator will notify the appropriate IRB/IEC/EC of SAEs occurring at the study site and other AE reports received from the Sponsor, in accordance with local procedures and statutes. The Investigator or designee at each study site is responsible for submitting Investigational New Drug (IND) safety reports (initial and follow-up) and other safety information (e.g., revised Investigator's Brochure) to the IRB/IEC/EC and for retaining a copy in the study files.

6.23. Adverse Events of Special Interest

The Investigator will monitor each subject for clinical and laboratory-evidence for predefined AEs of special interest (AESIs) throughout the subject's participation in this study. The Investigator should treat the AESI according to local standard of care. The following conditions will be monitored as AESIs during this study:

- Injection Site Reactions

- Diarrhea
- Hypoglycemia
- Neurological and Psychiatric Events
- Drug-induced liver injury

Drug-induced liver injury will be monitored and managed according to [Section 6.26](#).

During the course of the study, additional AESIs may be identified by the Sponsor. The Investigator will assess and record in detail any additional information for AESIs on the AE eCRF form.

Subjects who experience gastrointestinal adverse events while on study should be managed according to local standard of care including concomitant medications to manage symptoms.

6.24. Clinical Laboratory Abnormalities and Other Abnormal Assessments as Adverse Events or Serious Events

Laboratory abnormalities are usually not recorded as AEs or SAEs, however, laboratory abnormalities (e.g., clinical chemistry, hematology, urinalysis) independent of the underlying medical condition that require medical or surgical intervention or lead to investigational medicinal product interruption or discontinuation must be recorded as an AE, as well as an SAE, if applicable. In addition, laboratory or other abnormal assessments (e.g., electrocardiogram, X-rays, vital signs) that are associated with signs and/or symptoms must be recorded as an AE or SAE if they meet the definition of an AE (or SAE) as described in [Section 6.22](#). If the laboratory abnormality is part of a syndrome, record the syndrome or diagnosis (e.g., anemia) not the laboratory result (i.e., decreased hemoglobin). Severity should be recorded and graded according to the CTCAE Version 5.0. For AEs associated with laboratory abnormalities, the event should be graded based on the clinical severity in the context of the underlying conditions; this may or may not be in agreement with the grading of the laboratory abnormality.

Toxicity Management

Any questions regarding toxicity management should be directed to the Medical Monitor.

Grade 1 and 2 Laboratory Abnormality or Clinical Event

Continue investigational medicinal product at the discretion of the Investigator.

Grade 3 Laboratory Abnormality or Clinical Event

- For Grade 3 clinically significant laboratory abnormality or clinical event, investigational medicinal product may be continued if the event is considered to be unrelated to investigational medicinal product.

- For a Grade 3 clinical event, or clinically significant laboratory abnormality confirmed by repeat testing, that is considered to be related to investigational medicinal product, investigational medicinal product should be withheld until the toxicity returns to \leq Grade 2.
- If a laboratory abnormality recurs to \geq Grade 3 following re-challenge with investigational medicinal product and is considered related to investigational medicinal product, then investigational medicinal product should be permanently discontinued, and the subject managed according to local practice. Recurrence of laboratory abnormalities considered unrelated to investigational medicinal product may not require permanent discontinuation.

Grade 4 Laboratory Abnormality or Clinical Event

- For a Grade 4 clinical event or clinically significant Grade 4 laboratory abnormality confirmed by repeat testing, the DMC should perform a causality assessment. The investigational medicinal product may be restarted if the DMC concludes that the AE or laboratory abnormalities were not related to study drug, the AE has resolved, laboratory abnormalities have returned to baseline, and the subject is amenable to close clinical follow-up.
- If a laboratory abnormality recurs to \geq Grade 4 following re-challenge with investigational medicinal product and is considered related to investigational medicinal product, then investigational medicinal product should be permanently discontinued, and the subject managed according to local practice. Recurrence of laboratory abnormalities considered unrelated to investigational medicinal product may not require permanent discontinuation.
- If, after re-challenge, a subject has a second serious AE or recurrent elevations (even mild or minimal) of total bilirubin, ALT, or AST as defined in [Section 6.20](#), investigational medicinal product should be discontinued permanently.

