6.26.1. Subjects with Normal Liver Transaminases and Bilirubin at Baseline

Drug-induced liver injury monitoring in subjects with normal liver transaminases and bilirubin at baseline should be performed throughout the study according to the procedures summarized below.

- If subjects with normal baseline liver indices develop elevations in ALT of $>5 \times$ ULN during the study, repeat testing should be performed within 2 - 5 days from receipt of results.
 - If there are persistent elevations (ALT $>5 \times$ ULN or TBL $>2 \times$ ULN) upon repeat testing, close observation (testing and physical examination 2 to 3 times per week) should be implemented. An important purpose of the close observation is to gather additional clinical information to seek other possible causes of the observed liver test abnormalities, such as one of the following: acute viral hepatitis, alcoholic and autoimmune hepatitis, hepatobiliary disorders, cardiovascular causes, or concomitant treatments. Discontinuation of investigational medicinal product should be considered.
- Study drug should be discontinued, and the subject should be followed until resolution of signs or symptoms, in the following situations:
 - ALT $>8 \times$ ULN
 - ALT $>5 \times$ ULN and (TBL $>2 \times$ ULN)
 - ALT $>5 \times$ ULN with the appearance of fatigue, nausea, vomiting, right upper quadrant pain or tenderness, fever, rash, and/or eosinophilia ($>5\%$) as assessed by the PI to indicate hepatic injury

For any subjects who present with a constellation of syndromes indicative of liver disease as per the Investigator's overall assessment (i.e., fatigue, nausea, vomiting, right upper quadrant pain or tenderness, fever, rash, and/or eosinophilia [$> 5\%$]), perform liver function tests to determine if liver disease is worsening.

Re-initiation of investigational medicinal product may be considered after consultation with the Medical Monitor and DMC assessment.

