6.26.2. Subjects with Elevations in Liver Transaminases or Bilirubin at Baseline

Drug-induced liver injury monitoring in subjects with elevations in liver transaminases or bilirubin at baseline should be performed throughout the study according to the procedures summarized below.

- If subjects with abnormal baseline liver indices develop elevations of ALT $>3 \times$ baseline or ≥ 300 U/L (whichever occurs first) during the study, repeat testing should be performed within 2 - 5 days.

- If there are persistent elevations (ALT $>3 \times$ baseline, or ≥ 300 U/L) upon repeat testing, then close observation (testing and physical examination 2 to 3 times per week) should be implemented and discontinuation of study drug should be considered.
- Discontinue the study drug if any of the following occur:
 - ALT increases to $>5 \times$ baseline measurements or ≥ 400 U/L (whichever occurs first).
 - ALT increase $>3 \times$ baseline measurements or ≥ 300 U/L (whichever occurs first) AND the increase is accompanied by a concomitant increase in TBL to $> 2 \times$ ULN.
 - ALT increase $>3 \times$ baseline measurements or ≥ 300 U/L (whichever occurs first) with the appearance of fatigue, nausea, vomiting, right upper quadrant pain or tenderness, fever, rash, and/or eosinophilia ($> 5\%$)

For any subjects who present with a constellation of syndromes indicative of liver disease as per the Investigator's overall assessment (i.e., fatigue, nausea, vomiting, right upper quadrant pain or tenderness, fever, rash, and/or eosinophilia [$> 5\%$]), perform liver function tests to determine if liver disease is worsening.

Re-initiation of investigational medicinal product may be considered after consultation with the CRO Medical Monitor and DMC assessment.

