ALT	Alanine aminotransferase increased	>ULN - 3.0 x ULN if baseline was normal; 1.5 - 3.0 x baseline if baseline was abnormal	>3.0 - 5.0 x ULN if baseline was normal; >3.0 - 5.0 x baseline if baseline was abnormal	>5.0 - 20.0 x ULN if baseline was normal; >5.0 - 20.0 x baseline if baseline was abnormal	>20.0 x ULN if baseline was normal; >20.0 x baseline if baseline was abnormal
AST	Aspartate aminotransferase increased	>ULN - 3.0 x ULN if baseline was normal; 1.5 - 3.0 x baseline if baseline was abnormal	>3.0 - 5.0 x ULN if baseline was normal; >3.0 - 5.0 x baseline if baseline was abnormal	>5.0 - 20.0 x ULN if baseline was normal; >5.0 - 20.0 x baseline if baseline was abnormal	>20.0 x ULN if baseline was normal; >20.0 x baseline if baseline was abnormal
TBILI	Blood bilirubin increased	>ULN - 1.5 x ULN if baseline was normal; >1.0 - 1.5 x baseline if baseline was abnormal	>1.5 - 3.0 x ULN if baseline was normal; >1.5 - 3.0 x baseline if baseline was abnormal	>3.0 - 10.0 x ULN if baseline was normal; >3.0 - 10.0 x baseline if baseline was abnormal	>10.0 x ULN if baseline was normal; >10.0 x baseline if baseline was abnormal
ALP	Alkaline phosphatase increased	>ULN - 2.5 x ULN if baseline was normal; 2.0 - 2.5 x baseline if baseline was Abnormal	>2.5 - 5.0 x ULN if baseline was normal; >2.5 - 5.0 x baseline if baseline was Abnormal	>5.0 - 20.0 x ULN if baseline was normal; >5.0 - 20.0 x baseline if baseline was abnormal	>20.0 x ULN if baseline was normal; >20.0 x baseline if baseline was abnormal

CONFIDENTIAL

Statistical Analysis Plan

Sponsor Name: Akero Therapeutics, Inc.
 Sponsor Protocol ID: AK-US-001-0102

Serum Chemistry	CTCAE Term	Grade 1	Grade 2	Grade 3	Grade 4
Creatinine (Cr)	Creatinine increased	>ULN - 1.5 x ULN	>1.5 - 3.0 x baseline; >1.5 - 3.0 x ULN	>3.0 x baseline; >3.0 - 6.0 x ULN	>6.0 x ULN
CPK	CPK increased	>ULN - 2.5 x ULN	>2.5 - 5.0 x ULN	>5 - 10 x ULN	>10 x ULN
Potassium (K)	Hyperkalemia	>ULN - 5.5 mmol/L	>5.5 - 6.0 mmol/L	>6.0 - 7.0 mmol/L	>7.0 mmol/L
Amylase	Serum amylase increased	>ULN - 1.5 x ULN	>1.5 - 2.0 x ULN; >2.0 - 5.0 x ULN and NCS	>2.0 - 5.0 x ULN and CS; >5.0 x ULN and NCS	>5.0 x ULN and CS
Glucose	Hypoglycemia	<LLN - 55 mg/dL; <LLN - 3.0 mmol/L	<55 - 40 mg/dL; <3.0 - 2.2 mmol/L	<40 - 30 mg/dL; <2.2 - 1.7 mmol/L	<30 mg/dL; <1.7 mmol/L

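### For ALT rises that meet the Protocol 6.26 stop criteria but are below CTCAE Grade 4, Protocol 6.24 allows dosing to continue or resume where 6.20 and 6.26 require it to stop

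*Protocol*

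**What the plan says.** **Protocol 6.24, Toxicity Management**, assigns an action to each CTCAE v5.0 grade:

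- Grade 1 or 2: "Continue investigational medicinal product at the discretion of the Investigator".
- Grade 3, judged unrelated: "investigational medicinal product may be continued if the event is considered to be unrelated to investigational medicinal product".
- Grade 3, clinically significant, confirmed on repeat and "considered to be related to investigational medicinal product, investigational medicinal product should be withheld until the toxicity returns to" Grade 2 or lower. Nobody is named to approve resumption.
- Grade 4: "For a Grade 4 clinical event or clinically significant Grade 4 laboratory abnormality confirmed by repeat testing, the DMC should perform a causality assessment".

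**Protocol 6.26.1** (normal baseline) sets a repeat test for ALT above 5x ULN, then close observation if the rise persists, adding: "Discontinuation of investigational medicinal product should be considered". It requires a stop at ALT above 8x ULN, or above 5x ULN with bilirubin above 2x ULN or with symptoms that the investigator takes to indicate hepatic injury.

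**Protocol 6.26.2** (abnormal baseline) requires a stop at ALT above 5x baseline or at least 400 U/L. It also requires one at ALT above 3x baseline or at least 300 U/L when bilirubin exceeds 2x ULN or listed symptoms appear. On restart it says: "Re-initiation of investigational medicinal product may be considered after consultation with the CRO Medical Monitor and DMC assessment". 6.26.1 has a matching sentence.

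**Protocol 6.20** lists a Grade IV event, or meeting the 6.26 criteria, among the cases in which study drug must be stopped. Restart depends on the DMC concluding that the abnormality was unrelated and on values having returned to baseline, among other conditions.

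**Protocol 6.23** adds: "Drug-induced liver injury will be monitored and managed according to" Section 6.26.

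**SAP Table 6** gives Grade 3 ALT as ">5.0 - 20.0 x ULN if baseline was normal; >5.0 - 20.0 x baseline if baseline was abnormal".

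**The concern.** One ALT result can fall under two sets of instructions. An investigator who opens 6.24 and judges a Grade 3 rise unrelated finds express permission to keep dosing. One who opens 6.20 or 6.26 finds an instruction to stop that does not depend on that judgement.

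Withholding and discontinuing are also handled differently. Under Protocol 6.21 a subject whose dosing is interrupted should be kept in the study where possible. Under Protocol 3.3 discontinuation leads to an early termination visit and then the 30-day follow-up visit.

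What is at stake is consistent handling of a liver safety signal, and comparable recording of interruption and discontinuation across sites.

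**Working it through.** There is no stated figure to reproduce. The check grades each ALT band and sets the instructions side by side.

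**Inputs.** Grades are from SAP Table 6:

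- ALT: Grade 2 is >3 to 5x, Grade 3 is >5 to 20x and Grade 4 is >20x. The multiple is of ULN if baseline was normal and of baseline if it was abnormal.
- Bilirubin: Grade 2 is >1.5 to 3x ULN if baseline was normal. Inclusion criterion 3h makes that the usual case.

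| Band | Grade | 6.24 | 6.20 / 6.26 | Result |
|---|---|---|---|---|
| A. Normal baseline, ALT >8 to 20x ULN | 3 | May continue if unrelated; withhold to Grade 2 or lower if related | Stop | Contradiction |
| B. Abnormal baseline, ALT >5 to 20x baseline | 3 | As A | Stop | Contradiction |
| C. Abnormal baseline, ALT at least 400 U/L and no more than 5x baseline | 2 or lower | Investigator's discretion | Stop | Discretion against a required stop |
| D. Abnormal baseline, ALT >3 to 5x baseline, bilirubin >2 to 3x ULN | 2 for both | Investigator's discretion | Stop | Discretion against a required stop |
| E. Normal baseline, ALT >5 to 8x ULN, no bilirubin rise or symptoms | 3 | As A | Observe closely; consider stopping | Lesser mismatch |
| F. ALT >20x ULN or >20x baseline | 4 | DMC causality assessment | Stop; DMC | No conflict on the DMC step |

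For a normal baseline with ALT at or below 5x ULN, 6.26.1 has no ALT trigger, so nothing conflicts.

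**Which baselines reach band C.** An ALT of 400 U/L is no more than 5x baseline when baseline is at least 400 / 5 = 80 U/L. It is no more than 3x baseline, so at most Grade 1, when baseline is at least 400 / 3 = 133.3 U/L. For example, a rise from 100 to 400 U/L is 400 / 100 = 4.0x, Grade 2, and 6.26.2 requires a stop.

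Inclusion criterion 3l admits ALT below 5x ULN. The documents give no ULN in U/L. Assuming 30, 40 or 55 U/L, the eligibility ceiling is 5 x 30 = 150, 5 x 40 = 200 or 5 x 55 = 275 U/L. Baselines from 80 U/L up to that ceiling are therefore eligible. Bands A, B, D, E and F are stated in multiples and do not depend on this assumption.

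**Restart after a related Grade 3 rise.** Take a baseline of 60 U/L and a peak of 306 U/L: 306 / 60 = 5.1x, which is Grade 3 and a 6.26.2 stop.

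- Under 6.24, withholding ends at Grade 2, which is reached at 5 x 60 = 300 U/L.
- Under 6.20, restart needs values back at baseline and a DMC conclusion that the rise was not related.
- Under 6.26.2, it needs Medical Monitor consultation and DMC assessment.

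**Re-challenge.** 6.20 makes any second adverse event grounds for permanent discontinuation, whereas 6.24 requires a second serious one. For recurrent liver test elevations, 6.24 refers to 6.20 for the definition and 6.20 refers to 6.26.3. That section lists observation steps but gives no elevation threshold.

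**AST.** 6.24 covers AST through its grade, but 6.26.1 and 6.26.2 contain no AST threshold.

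**The case against.** The strongest reply is that 6.20 already settles the matter. Its wording is mandatory, and it is triggered by meeting the 6.26 criteria, not by a diagnosis of drug-induced liver injury. 6.23 points the same way, and 6.24 refers questions on toxicity management to the Medical Monitor. Where 6.24 only permits dosing, as in bands C and D, a site that stops complies with every section. In band E a site can withhold and observe closely, and so satisfy both texts.

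Much of this stands. A careful reader can infer that 6.20 and 6.26 control, and band E is not a case of opposite instructions.

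It does not remove the conflict. 6.24 states no such priority. Its Grade 4 text names ALT, AST and bilirubin, so it is meant to reach liver tests. At Grade 3 it expressly allows continuation after an unrelated rise, and after a related rise it sets an end to withholding that differs from the 6.20 restart conditions.

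A reader might also infer that the sections give opposite answers on who may restart dosing. They do not: 6.24 at Grade 3 names nobody, so it is silent where 6.20 and 6.26 are explicit.

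**Conclusion.** The contradiction is real for ALT rises that meet the 6.26 stop criteria but fall below Grade 4. It is plainest in bands A and B. In C and D, 6.24 leaves to discretion what 6.20 and 6.26.2 require. Band E is a lesser mismatch.

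This rests on two assumptions: that sites apply the CTCAE v5.0 grades as SAP Table 6 sets them out, and that the abnormality counts as clinically significant and is confirmed where 6.24 requires that. Band D also assumes a normal baseline bilirubin.

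Three stronger readings are tempting but unsupported:

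- That any raised ALT is affected. In normal-baseline subjects 6.26.1 has no ALT trigger at or below 5x ULN.
- That every ALT above 5x baseline lacks a DMC step in 6.24. Above 20x baseline the rise is Grade 4 and 6.24 does call for the DMC.
- That Week 24 biopsies or the primary analysis set would suffer. The documents give no incidence of such rises. Protocol 6.21 aims to keep interrupted subjects in study procedures, and Appendix A provides an early termination biopsy after at least 16 weeks of dosing.

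The point is one of safety consistency, with no demonstrated effect on the efficacy result.

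**What to change.** Reconcile Protocol 6.20, 6.23, 6.24 and 6.26:

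- Add a sentence to 6.24 stating which section governs ALT and bilirubin abnormalities that meet the 6.26 criteria.
- State which section covers AST.
- Align the restart conditions across 6.20, 6.24 and 6.26.
- Align the re-challenge wording of 6.20 and 6.24, and make the cross-reference for recurrent elevations end at an actual definition.

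Which rule stands is for the clinical team; this review takes no position. The cost is a protocol clarification, with no new procedures.
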